6.1. Statistical Definitions and Algorithms

6.1.1. Baseline

The last observation recorded before the first dose will be used as the baseline observation for all calculations of change from baseline.

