8.4.3 ADVERSE EVENTS OF SPECIAL INTEREST

Please note that for an event to be classified as an AE of special interest (AESI), the event should meet the definition of an Adverse Event per [Section 8.1.1](#). Thus, if the investigator considers the event to be an AE, and it meets one or more of the criteria listed below, then the event should be classified as an AESI and

reported according to the timeframe specified.

The following will be considered AEs of special interest (AESI) if they qualify as AEs per the preceding paragraph:

- Clinically significant peripheral edema or pulmonary edema.
- Clinically significant systolic BP >160 but <170 mmHg over consecutive timepoints spanning 30 or more minutes.
- Clinically significant systolic BP <90 or >170 mmHg at a single timepoint.
- Clinically significant diastolic BP >100 but <110 mmHg over consecutive timepoints spanning 30 or more minutes.
- Clinically significant diastolic BP <60 or >110 at a single timepoint.
- A change of >25% from baseline in systolic and/or diastolic BP.
- Reduced kidney function (eGFR < 45 mL/min/1.73 m²).
- Suspected transmission of blood-borne infectious agents.

AESI occurring during the study should be reported within 48 hours of observation or learning of the event, unless the event is serious, in which case the event must be reported according to the timeframes specified in [Section 8.4.2.1](#).

Note: Blood pressures meeting the parameters above that are not considered adverse events need not be reported within the 48-hour window. Rather, these will be considered “blood pressures of special interest” and analyzed separately.

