5.2. Prior to Infusion

The blinded Outcomes Assessor will check the following information prior to infusion start:

- a. Subject identification to ensure it is the correct subject.
- b. Verify eligibility criteria (e.g. subject’s history and diagnosis, including allergies and previous reactions to blood or blood products).
- c. Review AEs and concomitant medications.
- d. Baseline vital signs (temperature, seated BP, orthostatic BP, heart rate, respiratory rate, and weight) within 1 hour of the start of the infusion and record data on source document.

- e. Ensure Pre-Infusion Safety Lab and Comprehensive Lab samples are obtained when applicable per the [Schedule of Events](#). The results of the Pre-Infusion Safety Labs should be available and interpreted prior to the following day’s infusion.
- f. The PI or physician designee should perform a targeted physical exam when applicable per the [Schedule of Events](#).
- g. Review and interpret Pre-Infusion Safety Lab results. Refer to **Table 2. Signs or Symptoms Associated with Abnormal Lab Values**.
- h. Confirm with PI that the subject is cleared to begin the infusion.

Table 2. Signs or Symptoms Associated with Abnormal Lab Values

Lab abnormality	Signs and Symptoms	Additional Testing*
Hyponatremia	Lethargy, confusion, nausea, vomiting, muscle cramps or weakness	n/a
Hypokalemia	Weakness, fatigue, muscle cramps or heart palpitations	ECG: Increased amplitude and width of P wave, longer PR interval, T wave flattening, ST depression, prominent U waves
Hypocalcemia	paresthesia, circumoral numbness, laryngospasm, muscle spasms or muscle cramps	ECG: Narrowing QRS, shortening PR interval, T wave flattening, QT prolongation, prominent U-wave, ST depression
Hypoglycemia	Palpitations, dyspnea, confusion, fatigue, shakiness, sweating, irritability, tingling around the mouth, blurred vision, dizziness, sleepiness	n/a
Kidney failure (serum creatinine)	Decreased urine output, edema, drowsiness, fatigue, confusion, nausea, dyspnea	Urinalysis: proteinuria or albuminuria
Anemia (Hct or Hgb)	Dizziness, weakness, headache, cold extremities, numbness, low body temperature, pallor	n/a

*Additional testing may be performed as needed in the event that recent results aren’t available for review.

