5.3. During the Infusion (Safety Monitoring and Vital Signs)

During the infusion, the blinded Outcomes Assessor’s primary role is to observe the subject for AEs (refer to **Section 6: Monitoring for Adverse Reactions**) and to monitor vital signs (the unblinded Infusion Nurse is responsible for the administration of all infusions). If the subject is not tolerating an infusion well, the blinded Outcomes Assessor will instruct the unblinded Infusion Nurse to stop the infusion and will inform the PI or physician designee that the infusion has been stopped. **This should be done with care taken to not unblind the Outcomes Assessor, the PI, or his/her designee.** For example, if the subject is not tolerating the infusion well and the Blinded Outcomes Assessor asks the Unblinded Infusion Nurse to stop

the infusion, if the subject is receiving placebo, the Unblinded Infusion Nurse must be careful not to unintentionally convey this (e.g. acting surprised that the subject is not tolerating placebo).

The blinded Outcomes Assessor should follow the guidelines below for ALL INFUSIONS:

- a. Monitor and record baseline vital signs not more than one hour prior to infusion start.
- b. Once the infusion is started, record vital signs (seated BP, heart rate (HR), respiration rate (RR), temperature) every 15 minutes (\pm 5 minutes) for the first hour and then every 30 minutes (\pm 5 minutes) thereafter for as long as the infusion continues (up to [REDACTED]). Vital signs can also be recorded ad hoc if the subject is experiencing symptoms that indicate a change in vital signs.

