- PDQ-39 Emotional Well-Being subscore = sum of 6 items in the Emotional Well-Being domain (converted from a range of 0 [never] to 4 [always/cannot do at all] to a range of 0 to 100), divided by the maximum possible score on the scale and multiplied by 100.

- PDQ-39 Stigma subscore = sum of 4 items in the Stigma domain (converted from a range of 0 [never] to 4 [always/cannot do at all] to a range of 0 to 100), divided by the maximum possible score on the scale and multiplied by 100.
- PDQ-39 Social Support subscore = sum of 3 items in the Social Support domain (converted from a range of 0 [never] to 4 [always/cannot do at all] to a range of 0 to 100), divided by the maximum possible score on the scale and multiplied by 100.
- PDQ-39 Cognitions subscore = sum of 4 items in the Cognitions domain (converted from a range of 0 [never] to 4 [always/cannot do at all] to a range of 0 to 100), divided by the maximum possible score on the scale and multiplied by 100.
- PDQ-39 Communication subscore = sum of 3 items in the Communication domain (converted from a range of 0 [never] to 4 [always/cannot do at all] to a range of 0 to 100), divided by the maximum possible score on the scale and multiplied by 100.
- PDQ-39 Bodily Discomfort subscore = sum of 3 items in the Bodily Discomfort domain (converted from a range of 0 [never] to 4 [always/cannot do at all] to a range of 0 to 100), divided by the maximum possible score on the scale and multiplied by 100.
- PDQ-39 Total score = mean of all of the PDQ-39 subscores.
- GDS-15 Total score = sum of the 15 item questionnaire, with a range of 0 to 15. Each question is answered “yes” or “no”. Question numbers 1, 5, 7, 11, 13 indicate presence of depression when answered positively (yes) while the remaining questions indicate presence of depression when answered negatively (no). One point is counted for each depressive answer. A score of 0-4 indicates no depression, a score of 5-10 is suggestive of a mild depression, and a score of 11 or more is suggestive of severe depression.
- Modified Hachinski Ischemic Scale Total score = sum of the 8 item scores, with a range of 0-8.
- Change from baseline = value at current time point – value at baseline.
- TEAE = any adverse event with an onset date/time after first dose of medication.
- Disease duration (years) = [Enrollment date – PD onset date (as recorded on the Medical History case report form) + 1] / 365.25.

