9.3. Vital Signs

Descriptive summaries of actual values and changes from baseline will be calculated for seated systolic blood pressure, standing systolic blood pressure, and supine systolic blood pressure, seated diastolic blood pressure, standing diastolic blood pressure, and supine diastolic blood pressure, heart rate, respiration rate, and body temperature. These summaries will be presented by visit and treatment group. Vital signs are collected at all study visits. During the infusion periods (Visit 3-Visit 7 and Visit 11- Visit 15), orthostatic vital signs (supine systolic and supine diastolic blood pressure compared to standing systolic and standing diastolic blood pressure) should be measured prior to infusion start and at approximately [REDACTED] after infusion start. Seated systolic and seated diastolic blood pressure is measured at multiple timepoints during and after each infusion. Abnormal vital sign values will be flagged in the listings. Abnormal vital sign values are as follows:

- Seated systolic blood pressure value < 90 mmHg
- Seated systolic blood pressure value > 180 mmHg
- Seated diastolic blood pressure value < 50 mmHg
- Seated diastolic blood pressure value > 110 mmHg
- Incidence of orthostatic hypotension (a decrease in systolic blood pressure of > 20 mm Hg and/or a decrease in diastolic blood pressure of > 10 mm Hg between supine and standing)
- Heart rate > 100 beats per minute
- Temperature > 37.5°C
- Temperature < 36.5°C
- Respiration rate > 20 breaths per minute
- Respiration rate < 12 breaths per minute

The vital sign measurements that meet the criteria for blood pressures of special interest (listed below) will also be identified from the vital signs source data and summarized separately by study visit, timepoint, and treatment.

- Seated systolic blood pressure >180 mmHg
- Seated systolic blood pressure > 200 mmHg
- Seated systolic blood pressure < 90 mmHg
- Seated diastolic blood pressure > 110 mmHg
- Seated diastolic blood pressure > 120 mmHg
- Seated diastolic blood pressure < 50 mmHg
- A change of $\geq 30\%$ from baseline in seated systolic and/or seated diastolic blood pressure

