Sponsor Alkermes, Inc.
Protocol Number ALK6021-201
PCN Number ALKA7951

Table 14.3.6.1.1
Summary of Vital Signs by Study Visit and Treatment
Safety Set

(Same shell as Table 14.3.5.1.1; visits include Visit 1- Visit 19; parameters include Temperature (C), Respiration Rate (breaths per min), Sitting Systolic Blood Pressure (mmHg), Standing Systolic Blood Pressure (mmHg), and Supine Systolic Blood Pressure (mmHg), Heart Rate (bpm), Sitting Diastolic Blood Pressure (mmHg), Standing Diastolic Blood Pressure (mmHg), and Supine Diastolic Blood Pressure (mmHg), Weight (kg); SOURCE: Listing 16.2.8.2.)

Statistical Analysis Plan,
Sponsor Alkermes, Inc.
Protocol Number ALK6021-201
PCN Number ALKA7951

Table 14.3.6.1.2
Summary of Blood Pressures of Special Interest by Study Visit and Treatment Safety Set

Study Visit Category	Placebo (N=XX) n (%)	GRF6021 (N=XX) n (%)	Overall (N=XX) n (%)
Parameter: XXXXXXXXX			
Baseline [1]			
SBP > 180mmHg	XX (XX.X%)	XX (XX.X%)	XX (XX.X%)
SBP > 200 mmHg	XX (XX.X%)	XX (XX.X%)	XX (XX.X%)
SBP < 90 mmHg	XX (XX.X%)	XX (XX.X%)	XX (XX.X%)
Week 1 (Visit 3) 15 MIN DURING INFUSION			
SBP > 180mmHg	XX (XX.X%)	XX (XX.X%)	XX (XX.X%)
SBP > 200 mmHg	XX (XX.X%)	XX (XX.X%)	XX (XX.X%)
SBP < 90 mmHg	XX (XX.X%)	XX (XX.X%)	XX (XX.X%)
CFB ≥ 30%	XX (XX.X%)	XX (XX.X%)	XX (XX.X%)
Week 1 (Visit 3) 30 MIN DURING INFUSION			
SBP > 180mmHg	XX (XX.X%)	XX (XX.X%)	XX (XX.X%)
SBP > 200 mmHg	XX (XX.X%)	XX (XX.X%)	XX (XX.X%)
SBP < 90 mmHg	XX (XX.X%)	XX (XX.X%)	XX (XX.X%)
CFB ≥ 30%	XX (XX.X%)	XX (XX.X%)	XX (XX.X%)

Continue for other parameters. Sort alphabetically by parameter.

Abbreviations: CFB = change from baseline; DBP = diastolic blood pressure; SBP = systolic blood pressure.
 Note: Percentages are n/Number of subjects in the Safety Set*100. Subjects are summarized by treatment received. Blood pressures of special interest are as follows: seated systolic blood pressure > 180 mmHg, seated systolic blood pressure > 200 mmHg, seated systolic blood pressure < 90 mmHg, seated diastolic blood pressure >110 mmHg, seated diastolic blood pressure > 120 mmHg, seated diastolic blood pressure < 50 mmHg, or a change of ≥ 30% from baseline in seated systolic and/or seated diastolic blood pressure.
 [1] The baseline value for each variable is the value recorded prior to the first dose.
 SOURCE: Listing 16.2.8.1.3

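### From Day 2 on, the SAP's blood pressure change values and ≥30% flag at infusion timepoints mix acute change with between-day variation, because the only reference is the pre-first-dose reading

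*SAP*

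**What the plan says.** SAP 6.1.1 gives a single rule: "The last observation recorded before the first dose will be used as the baseline observation for all calculations of change from baseline". SAP 6.1.7 builds the difference on it ("Change from baseline = value at current time point" minus the value at baseline). SAP 9.3 makes no exception for infusion days. One of its criteria for a blood pressure of special interest is a change of at least 30% "from baseline in seated systolic and/or seated diastolic blood pressure", and these readings are to be "summarized separately by study visit, timepoint, and treatment". The shell of Table 14.3.6.1.2 has rows at 15 and 30 minutes into the infusion, each with a ≥30% change category, and its footnote says "The baseline value for each variable is the value recorded prior to the first dose". Table 14.3.6.1.1 (vital signs) borrows a laboratory shell with the same footnote. Nothing resets the reference at Visit 11 or at any other infusion.

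The Infusion Administration Manual (Protocol Appendix 11) uses the word differently. Its section 5.2 asks for "Baseline vital signs (temperature, seated BP, orthostatic BP, heart rate, respiratory rate, and weight) within 1 hour of the start of the infusion", and section 5.3, which covers all infusions, says "Monitor and record baseline vital signs not more than one hour prior to infusion start". Protocol 8.4.3 lists among the adverse events of special interest "A change of >25% from baseline in systolic and/or diastolic BP" and does not say which baseline it means.

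**The concern.** A table by infusion timepoint is there to show what happens to blood pressure during and after an infusion. The natural reference for that is the reading taken just before the same infusion. With the pre-first-dose reading as the only reference, the computed change on any later day is the sum of the acute change and the difference between that day's starting pressure and Day 1's. In the second course that difference can include three months of drift.

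Hypotension is among the important identified risks in Protocol 2.3.1, and change in vital signs is a secondary safety endpoint. Protocol 8.4.3 sends readings that meet its blood pressure parameters but are not judged adverse events to a separate analysis of blood pressures of special interest. For those readings, individual misclassification matters.

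**Working it through.** The documents give no figure on this point, so there is nothing to reproduce. The check has three steps.

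**1. Age of the reference.** The courses start on Day 1 and Day 85 ± 7 (Protocol 7.3.4). (85 − 1)/7 = 12 weeks; the window gives (78 − 1)/7 = 11 to (92 − 1)/7 = 13 weeks. On Day 1 the SAP reference is normally the same-day pre-infusion value, so the problem starts on Day 2.

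**2. Two arithmetic examples** (seated systolic, mmHg; the values are illustrative). Percent change = (reading − reference)/reference.

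| | Day 1 pre-dose | Day 85 pre-infusion | During infusion | Same-day change | Change under the SAP | SAP flag |
|---|---|---|---|---|---|---|
| Missed fall | 120 | 150 | 102 | (102 − 150)/150 = −32% | (102 − 120)/120 = −15% | None (102 is not <90) |
| Non-acute reading | 150 | 110 | 104 | (104 − 110)/110 = −5.5% | (104 − 150)/150 = −30.7% | Flagged |

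**3. Simulation for size.** All variances are assumptions; the documents give none. Model: reading = subject mean + day effect + reading error. Systolic mean 130, between-subject SD 14, day-to-day SD 8 to 12, reading SD 6.

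- *False flags* (no infusion effect, days after Day 1, flag if |reading/reference − 1| ≥ 0.30): about 1.2% of individual readings at day-to-day SD 8 and about 5.0% at SD 12 with the pre-first-dose reference, against 0.02% to 0.03% with the same-day reference. This is the per-timepoint level at which the SAP tabulates.
- *Missed falls* (reading = 0.65 × same-day pre-infusion value): the ≥30% rule alone flags about 69% to 75%. A 35% fall from 130 is 84.5, so the <90 cut-off in the same SAP list catches part of the rest. With it, 84% to 88% are flagged and 12% to 16% are not.

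A wider set of assumptions gives the same direction. The systolic scenarios use mean 130, between-subject SD 15, and day-to-day/reading SDs of 6/5, 10/6 and 15/8. The diastolic scenarios use mean 78, between-subject SD 8, and SDs of 4/4, 7/5 and 10/6.

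| | False flags per reading, pre-first-dose reference | Same-day reference | Acute falls of 30-40% unflagged after the <90 / <50 floor |
|---|---|---|---|
| Systolic | 0.2% / 2.8% / 11.7% | <0.1% / <0.1% / 0.4% | 11% / 15% / 20% |
| Diastolic | 0.8% / 6.6% / 16.5% | 0.1% / 0.4% / 1.6% | 19% / 25% / 28% |

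**The case against.** Several points on the other side stand.

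- **Scope.** A reader might infer that every infusion-day blood pressure measure is compromised. The documents do not support that. SAP 9.3 also has absolute cut-offs (systolic <90, >180, >200; diastolic <50, >110, >120) and a supine-to-standing criterion, and it summarises actual values. SAP 9.1.3 tabulates blood-pressure adverse events by infusion period. None of these uses this baseline.
- **Unused data.** A reader might infer that the later pre-infusion readings are discarded. They are not: all collected data are listed (SAP 6.1.8). Where pre-infusion and later means are both tabulated on the same subjects, the fixed baseline cancels and the mean acute change can be recovered. The individual ≥30% classification cannot.
- **Bias.** A reader might infer a spurious drug effect. Both randomised arms carry the same noise, and Table 14.3.6.1.2 is a descriptive count without a test. The harm is dilution.
- **A first-infusion reference has a purpose.** Table 3 of the manual defines sustained hypotension and hypertension as absent before the first infusion, so the manual uses both kinds of reference. Over five daily infusions of a product with a volume-overload concern, change from the pre-first-dose value shows cumulative drift, which a daily reset would hide. Replacing the SAP reference would therefore lose information.
- **Protocol 8.4.3.** Adverse events of special interest rest on the investigator's judgement, and nothing shows that the SAP definition governs site reporting. The undefined baseline there is a separate wording gap.

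**Conclusion.** The point holds for individual change-from-baseline values and for the ≥30% flag at during- and post-infusion timepoints, from Day 2 on and most at Visits 11-15. Followed as written, the SAP will leave some acute falls unflagged and flag some readings that involve little acute change. The mechanism follows from the SAP text and the two examples, and needs no assumption about variances.

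The size does depend on assumptions. For systolic pressure with day-to-day SD 8 to 12, it is about 1.2% to 5.0% of readings falsely flagged against about 0.03%, and 12% to 16% of 35% falls unflagged after the <90 cut-off. The wider scenarios show how far these move, so they should be read as illustrations. Higher per-day or per-subject false-flag rates can be produced by pooling many readings, but the SAP shell has no such row and the infusion duration that sets the number of readings is redacted.

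This is a cheap improvement to a safety display. It does not threaten the validity of the primary adverse event analysis.

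**What to change.** In SAP 6.1.1, SAP 9.3 and Tables 14.3.6.1.1 and 14.3.6.1.2, add a second reference. For all during- and post-infusion seated readings at Visits 3-7 and 11-15, also report change, percent change and the ≥30% count relative to that day's pre-infusion seated value. Keep the pre-first-dose reference beside it for between-visit change and cumulative drift, and label each column or row with its reference.

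Separately, reconcile which baseline the percent-change criterion in Protocol 8.4.3 means, given the per-infusion baseline in sections 5.2 and 5.3 of the manual and the pre-first-dose baseline in the SAP.

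The cost is SAP wording, one derived variable and extra table rows. The readings are already required before every infusion, so sites and subjects carry no added burden.

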6.1.2. Adjustments for Covariates

If there is a statistical difference among treatment groups with respect to baseline characteristics or values, that variable may be added to the statistical models as covariate to determine the effect on treatment. Baseline scores will be added as a covariate in models to assess efficacy.

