10.4 DESCRIPTION OF STATISTICAL METHODS

10.4.1 GENERAL APPROACH

Using the Evaluable and/or Per Protocol Datasets, all secondary endpoints will be summarized serially over time using descriptive statistics to assess the within-subject changes and between-group differences. Overall baseline and demographic data will be summarized using descriptive statistics; between-groups testing will be used to evaluate the effectiveness of the randomization in producing homogeneous pre-treatment groups.

For analysis of the primary and secondary endpoints, the following will be considered:

- For endpoints that are continuous in nature:
 - Number of observations, mean, median, minimum and maximum, and standard deviation (SD) values will be presented as descriptive summary
 - For inferential statistics:
 - If the Normality assumption is met, Paired t-test, or Analysis of Covariance (ANCOVA) using the baseline value as a covariate will be used
 - If the Normality assumption is not met, a rank –ANCOVA analysis i.e., an ANCOVA analysis on rank-transformed data or other non-parametric methods will be used
- For endpoints that are categorical in nature:
 - Frequency counts and percentages will be presented as descriptive summary
 - Chi-square test or Logit model will be used for inferential statistics

Subject disposition (e.g., the number of subjects randomized, completed, and discontinued) will be summarized, and medical history data will be listed. Prior and concomitant medications taken from screening and during the study will be categorized by World Health Organization classification for therapeutic class and drug name, listed and summarized by number and percentage of subjects.

Final analyses are not limited to the summaries described herein. As noted above, analytical details and assumptions will be fully presented in the SAP.

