4.1. Introduction

Data processing, tabulation of descriptive statistics, calculation of inferential statistics, and graphical representations will be performed primarily using SAS (release 9.4 or higher). If the use of other software is warranted, the final statistical methodology report will detail what software was used for what purposes.

Continuous (quantitative) variable summaries will include the number of subjects (n) with non-missing values, mean, standard deviation (SD), median, minimum, and maximum.

Categorical (qualitative) variable summaries will include the frequency and percentage of subjects who are in the particular category or each possible value. In general, the denominator for the percentage calculation will be based upon the total number of subjects in the study population for each treatment group, unless otherwise specified. The denominator for by-visit displays will be the number of subjects in the relevant study population with non-missing data at each visit.

The minimum and maximum will be reported with the same degree of precision (i.e., the same number of decimal places) as the observed data. Measures of location (mean and median) will be reported to 1 degree of precision more than the observed data and measures of spread (SD) will be reported to 2 degrees of precision more than the observed data.

Percentages will be presented to 1 decimal place, unless otherwise specified. Percentages will not be displayed when the numerator for a cell is 0.

Unless otherwise indicated, all statistical tests will be conducted at the 0.05 significance level using 2-tailed tests, and *P* values will be reported. Corresponding 95% CIs will be presented for statistical tests.

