7.3. Demographics and Other Baseline Characteristics

Summary statistics for age, sex, race, ethnicity, height, weight, disease duration, and apolipoprotein E (ApoE) genotype will be presented by treatment group using summary statistics or frequencies, as appropriate. See Section 6.1.7 for derivation of disease duration.

The means of continuous demographic variables will be tested using Wilcoxon rank-sum test and the proportions of categorical demographic variables will be tested using a Chi-square test or Fisher's Exact test, as appropriate, in order to evaluate the effectiveness of the randomization in producing homogeneous pre-treatment groups.

These analyses will be conducted for the ITT Set.

The number and percent of subjects reporting various medical histories grouped by MedDRA system organ class and preferred term, will be tabulated. Medical histories of Parkinson's disease will also be presented by SOC, PT, and lower level term (LLT). Subject and family medical history as well as tobacco smoking, alcohol, and illicit substance use will be listed. Social history and exercise level will also be listed.

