8.2.1. Montreal Cognitive Assessment (MoCA)

The MoCA is a 1-page, 30-point test designed as a rapid screening instrument for mild cognitive dysfunction. The questionnaire assesses several different cognitive domains, including attention and concentration, executive functions, memory, language, visuospatial skills, conceptual thinking, calculations, and orientation. Higher scores indicate better cognitive function; the total possible score is 30 and a score of 26 or more is considered normal. Derivation for the MoCA total score is described in Section 6.1.7.

The MoCA will be collected at Screening (Visit 1), Week 4 (Visit 9), and Week 16 (Visit 17).

Change from baseline to study visit in the MoCA total score and individual domains will be summarized by treatment group. Boxplots of the MoCA total score will also be provided by treatment group and visit. A test of hypothesis comparing mean total scores between baseline and subsequent study visits will be conducted using a 2-sided paired t-test or Wilcoxon signed

rank test, as appropriate. The null hypothesis is that the change from baseline to subsequent visit is 0.

Additionally, the mean change from baseline in MoCA total score will be compared between treatment groups using an ANCOVA model with treatment, visit, and treatment by visit interaction as a main effects and baseline MoCA total score, age, and ApoE genotype as covariates.

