P value [1]		X.XXXXX	
Weight (kg)			
n	XX	XX	XX
Mean (SD)	XX.X (XX.X)	XX.X (XX.X)	XX.X (XX.X)
Median	XX.X	XX.X	XX.X
Min, Max	XX, XX	XX, XX	XX, XX
P value [1]		X.XXXXX	
Body Mass Index (kg/m²)			
n	XX	XX	XX
Mean (SD)	XX.X (XX.X)	XX.X (XX.X)	XX.X (XX.X)
Median	XX.X	XX.X	XX.X
Min, Max	XX, XX	XX, XX	XX, XX
P value [1]		X.XXXXX	

Abbreviations: ApoE = apolipoprotein E; CRF = case report form; PD = Parkinson's Disease.
Note: Percentages are n/Number of subjects in the ITT Set*100. Subjects are summarized by randomized treatment. Disease duration = [Enrollment date – PD onset date (as recorded on the Medical History CRF) + 1] / 365.

[1] P value from Wilcoxon rank-sum test.

[2] P value from Chi-square test.

[3] Only captured for female subjects; percentages are based on the number of female subjects in the ITT Set.

[4] Obtained from Visit 3 blood draw.

Source: Listing 16.2.4.1

Table 14.1.2 (cont.)
Demographics and Baseline Characteristics
ITT Set

Variable Statistic or Category	Placebo (N=XX)	GRF6021 (N=XX)	Overall (N=XX)
Disease Duration (years)			
n	XX	XX	XX
Mean (SD)	XX.X (XX.X)	XX.X (XX.X)	XX.X (XX.X)
Median	XX.X	XX.X	XX.X
Min, Max	XX, XX	XX, XX	XX, XX
P value [1]		X.XXXX	
ApoE Genotype [4]			
2/2	XX (XX.X%)	XX (XX.X%)	XX (XX.X%)
2/3	XX (XX.X%)	XX (XX.X%)	XX (XX.X%)
3/3	XX (XX.X%)	XX (XX.X%)	XX (XX.X%)
4/3	XX (XX.X%)	XX (XX.X%)	XX (XX.X%)
4/4	XX (XX.X%)	XX (XX.X%)	XX (XX.X%)
2/4	XX (XX.X%)	XX (XX.X%)	XX (XX.X%)
P value [2]		X.XXXX	

Abbreviations: ApoE = apolipoprotein E; CRF = case report form; PD = Parkinson's Disease.
 Note: Percentages are n/Number of subjects in the ITT-Set*100. Subjects are summarized by randomized treatment. Disease duration = [Enrollment date – PD onset date (as recorded on the Medical History CRF) + 1] / 365.
 [1] P value from Wilcoxon rank-sum test.
 [2] P value from Chi-square test.
 [3] Only captured for female subjects; percentages are based on the number of female subjects in the ITT Set.
 [4] Obtained from Visit 3 blood draw.
 Source: Listing 16.2.4.1

Programming Note: If cell counts are <5, use Fisher's Exact Test and update footnote accordingly.

Statistical Analysis Plan,
Sponsor Alkermes, Inc.
Protocol Number ALK6021-201
PCN Number ALKA7951

Table 14.1.3.1
Summary of Medical History by SOC, PT, and Treatment
Safety Set

System Organ Class Preferred Term	Placebo (N=XX)	GRF6021 (N=XX)	Overall (N=XX)
Subjects with at least 1 Recorded Medical History	XX (XX.X%)	XX (XX.X%)	XX (XX.X%)

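### SAP 6.1.2 lets a significant baseline difference between arms add a covariate to the efficacy models, while sex, the stratification factor, is in none of them

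*SAP*

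**What the plan says.** SAP 6.1.2 has two sentences. The first reads "If there is a statistical difference among treatment groups with respect to baseline characteristics or values, that variable may be added" to the models, so as to see what it does to the treatment effect. The second puts the baseline score into the efficacy models. The section gives no list of candidates, no threshold, no timing and no decision-maker, and it does not say how the extended fit is to be labelled. The threshold comes by default from SAP 4.1: "all statistical tests will be conducted at the 0.05 significance level using 2-tailed tests".

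SAP 7.3 plans the between-arm baseline tests: "Summary statistics for age, sex, race, ethnicity, height, weight, disease duration, and apolipoprotein E (ApoE) genotype will be presented by treatment group", with Wilcoxon, chi-square or Fisher tests "in order to evaluate the effectiveness of the randomization in producing homogeneous pre-treatment groups". It adds: "These analyses will be conducted for the ITT Set". The Table 14.1.2 shell also prints a P value for "Body Mass Index", which makes nine. Protocol 10.4.1 makes the same commitment to testing ("between-groups testing will be used to evaluate the effectiveness of the randomization in producing homogeneous pre-treatment groups") but does not link the tests to the choice of model.

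The models are specified elsewhere. SAP 8.2.1 has "baseline MoCA total score, age, and ApoE genotype as covariates". The D-KEFS, CISI-PD, PDQ-39 and dCDT sections follow the same pattern, and MDS-UPDRS (8.2.4) uses baseline score and age only. SAP 3.5 stratifies randomisation by sex.

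**The concern.** A covariate earns its place in an ANCOVA by predicting the outcome. A between-arm P value at baseline does not measure that. In a properly randomised trial it measures only how uneven the draw happened to be, so a weak variable can qualify and a strong one can fail to.

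The trigger also needs arm-level data. SAP 3.6 keeps the sponsor blinded through database lock apart from designated staff and the interim statistician, so the decision comes after lock or draws on the unblinded interims, for both of which SAP Table 2 flags the demographics table. The word may leaves two possible treatment estimates for an endpoint, with the second available only once the arms have been compared.

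The SAP expects efficacy trends from this trial to inform the sample size of later studies, so it should be clear beforehand which estimate is the planned one. The factor with the clearest design reason to be in the models, sex, is left out.

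**Working it through.** **1. The plan's own figure.** Protocol Summary: 90 randomised, 25% drop-out. 90 × (1 − 0.25) = 67.5, which reproduces the stated 68 or so evaluable subjects. At 2:1 that is 68 × 2/3 ≈ 45 on GRF6021 and 68 × 1/3 ≈ 23 on placebo.

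**2. Candidate variables.** The Table 14.1.2 shell tests age, sex, ethnicity, race, height, weight, BMI, disease duration and ApoE. Age and ApoE are already in most models and sex is stratified, which leaves 9 − 3 = 6: ethnicity, race, height, weight, BMI and disease duration. MDS-UPDRS has no ApoE term, so there are 7.

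**3. Chance of at least one false trigger.** With sound randomisation and k independent tests at 0.05, this is 1 − 0.95^k.
- k = 6: 1 − 0.735 = 0.265
- k = 7: 1 − 0.698 = 0.302

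Height, weight and BMI are correlated, so the true values for these tests are somewhat lower. A trigger permits an addition and does not require it.

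**4. Does the trigger track prognostic value?** Null simulation: 45 against 23 subjects, six independent covariates, rank-sum screen at 0.05, 6,000 runs per row. The correlation of each covariate with outcome (rho) is an assumption, because the documents give none.

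| rho | any trigger | type I error, unadjusted | type I error, rule always followed | type I error, better of the two P values | significance call differs |
|---|---|---|---|---|---|
| 0 | 26.8% | 5.1% | 5.0% | 5.4% | 0.7% |
| 0.2 | 26.7% | 4.7% | 4.1% | 5.2% | 1.6% |
| 0.35 | 25.8% | 5.5% | 3.5% | 5.8% | 2.7% |

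The trigger fires about equally often for useless and for prognostic covariates. Followed mechanically, the rule is conservative. Picking the better P value adds 0.3 to 0.5 percentage points to the unadjusted rate in the same runs (5.4 − 5.1, 5.2 − 4.7, 5.8 − 5.5).

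**5. Consistency of the SAP with itself.** The Table 14.2.1.2 footnote states the MoCA model in full, with baseline score, age and ApoE as its covariates. The other ANCOVA tables reuse that shell, including GDS-15, for which Section 8.2.8 describes no ANCOVA. The MDS-UPDRS shell notes rule out any covariate beyond age and baseline score. Section 6.1.2 allows more, and no table is planned for an extended model.

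**6. Sex.** It is the stratification factor in SAP 3.5 and Protocol 10.6.1, but appears in no covariate list in Section 8.2 and not in the shell footnote. The CDR-CCB models are in a separate plan and were not checked.

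**The case against.** The best defence is that the main models are not open. Baseline score and age are fixed for every ANCOVA described in Section 8.2, ApoE for all but MDS-UPDRS, and the shells carry those models into the tables. The extra covariate is optional, and its stated purpose can be read as a sensitivity check. SAP Section 1 requires unplanned analyses to be identified as such in the study report. Efficacy is secondary and unpowered, and the primary safety analysis has no covariate model.

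Most of this stands. A reader might infer that nothing determines which model is reported, or that established predictors stay out unless they happen to be imbalanced. The documents do not support either reading, because the shells fix the tabulated model and the named predictors are always included.

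What the defence does not remove is the sentence itself. An addition made under 6.1.2 is foreseen by the SAP, so the rule on unplanned analyses need not catch it. Section 6.1.2 does not call the result a sensitivity analysis, and for MDS-UPDRS it contradicts the shell outright.

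**Conclusion.** The point holds in a limited form. One permissive sentence makes an optional extra covariate depend on chance imbalance and unblinded data. It conflicts with the rest of the SAP, and the stratification factor is missing from the models. The chance of at least one false trigger is at most about 26% for the six variables and about 30% for the seven, counting only the Table 14.1.2 tests at the default 0.05 level. The effect on type I error is small under the assumed correlations.

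Three stronger readings are tempting, and the documents do not support them:
- **A 37% trigger rate.** 1 − 0.95^9 = 0.370 counts all nine P values, including age and ApoE, which most models already contain, and sex, which is stratified.
- **A large loss of power.** In a simulation with a predictor correlated 0.5 with outcome and a 0.7 SD effect (both assumed), power was 0.770 never adjusting, 0.778 under the rule and 0.866 always adjusting. The rule costs nothing against never adjusting. The gap to 0.866 is the gain from a predictor that neither the rule nor the fix is shown to supply, and at a correlation of 0.3 it shrinks to 0.770 against 0.804.
- **Imbalance tested in the wrong population.** Section 7.3 tests the ITT Set and the models use narrower sets, but 6.1.2 does not tie its trigger to Table 14.1.2. The SE-ADL shell also prints a baseline P value on the Evaluable Set. The mismatch is possible but not stated.

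**What to change.** - Delete the first sentence of SAP 6.1.2 and keep the second.
- Keep the covariates already named in Section 8.2, including the MDS-UPDRS set without ApoE unless a reason for adding it is given.
- Add sex, as the stratification factor, to each ANCOVA, and update the shell footnotes and the MDS-UPDRS notes to match.
- Name any further covariate before database lock on prognostic grounds, and report that fit as a labelled sensitivity analysis beside the planned one.
- State that baseline P values do not drive model choice. If they are dropped from Table 14.1.2, record the departure from Protocol 10.4.1 in SAP Section 10, because the testing is a protocol commitment.

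The cost is one degree of freedom per model for sex and minor SAP wording. No extra data are needed.
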